7.9.2. Key Secondary Efficacy Parameters

There are 3 key secondary efficacy parameters which will be included in the hypothesis testing procedure.

- 1. Change from Baseline at Week 8 in WRFS
 - The WRFS is an average of the non-missing Daily Regurgitation Frequency Scores (DRFS) for that week (Appendix 1).
 - The DRFS for a day is the greater score of the 2 mRESQ-eD items assessing regurgitation frequency ("Regurgitation [liquid or food moving upwards toward your throat or mouth]" and "An acid or bitter taste in the mouth") for that day. Where 1 of the 2 mRESQ-eD regurgitation frequency items is missing for the day, the maximum will be the score of the remaining item; where both of the items are missing for the day, the DRFS will be missing.
- 2. Overall Heartburn Responder (OHR)
 - An OHR is a patient who is a Weekly Heartburn Responder for at least 4 weeks, including at least 1 of the last 2 weeks (Weeks 7 and 8), during the 8-week Treatment Period.
 - A patient who reports a DHSS for less than 4 days during a week will be considered a non-responder for that week.
 - A Weekly Heartburn Responder is a patient with a decrease of ≥45% from baseline in WHSS.

- 3. Proportion of heartburn-free days during the 8-week Treatment Period
 - Proportion of heartburn-free days is calculated as the number of heartburn-free (DHSS = 0) days divided by the number of diary entry days (Appendix 1).

7.9.2.1. Analysis of the Secondary Efficacy Parameters

If the primary efficacy comparison generates a superiority result for IW-3718, the secondary efficacy parameters will be tested and so on. The testing order and analysis methods are listed below:

Order of Hypothesis Testing	Parameters	Analysis Method and Outputs	Assumptions
1	Change from Baseline at Week 8 in WRFS	Efficacy parameter WRFS will be analyzed using the MMRM approach like the primary efficacy parameter, WHSS change from baseline.	MAR
2	Overall Heartburn Responder	The proportions of responders between the IW-3718 group and the placebo group will be compared using a Cochran-Mantel-Haenszel (CMH) test controlling for baseline EE status (present vs. not present), baseline WHSS (<3 vs. \geq 3). The CMH test is the primary analysis for responder parameters. The estimated odds ratio (IW-3718 over placebo) associated 95% CI and P value based on CMH test will be tabulated. Additionally, difference in responder rate with a 95% Newcombe CI (3) will also be provided.	Missing will not be imputed.
3	Proportion of Heartburn-free Days During the 8-week Treatment Period	The data will be analyzed using the Poisson regression, which is appropriate for count data. The analysis includes the fixed categorical effect of treatment, the baseline esophagitis status (present vs. not present) and baseline WHSS ($\langle 3 vs. \geq 3 \rangle$), the covariate of baseline proportion of heartburn-free days, and with the diary entry duration (in days) as a weight variable ^a adjusted in the model. Model estimates in difference of incidence rate between the IW-3718 treatment group and placebo will be represented with corresponding 95% CI and P -value associated with the comparisons to placebo. In the case of overdispersion, a negative binomial model instead of Poisson regression will be implemented.	Data following a Poisson distribution. Missing data will not be imputed.

 Table 6:
 Analysis and Assumptions of the Secondary Efficacy Parameters

a. The weight variable weights the overdispersion parameter, which has the default value of 1. The weight variable does not have to be an integer, if it is less than or equal to 0 or if it is missing, the corresponding observation is not used for modeling analysis.

Like the primary efficacy parameter, a corresponding line graph of LS mean with 95% CI by treatment group and Week for WRFS will be presented. CDF of change from baseline at Week 8 in WRFS to be plotted by treatment group. To aid in the interpretation of the graphical representation of the CDF across treatment group, a 2-sample Kolmogorov-Smirnov test will be conducted.

CDF plots of change from Baseline at each week in WRFS by treatment group and patientreported weekly Degree of Relief Assessments (comparing the symptoms over the past 7 days, Appendix 7) classified anchor will be provided. For a sense of variability in the distribution of the classified heartburn relief anchor category, percentile (10th, 25th, 75th and 90th) of change from Baseline to each week in WRFS by treatment group and the anchor will be tabulated.

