7.9.3. Exploratory Efficacy Parameters

Exploratory efficacy parameters will be explored outside of the formal testing procedures and not controlled for multiplicity. The mITT Population will be used for the analyses. If appropriate, for selected efficacy parameters, the SA Population will be used for sensitivity analysis. The baseline definitions for different type of parameters can be found in Section 7.9.

- Change or percent change continuous parameters will be analyzed using the MMRM approach like the primary efficacy parameter, WHSS change from baseline.
- Categorical responder parameters will be analyzed utilizing the CMH testing method that is proposed for the secondary efficacy analysis for OHR.
- Time dependent proportion parameters, defined as days the event of interesting occurs divided by the number of eDiary entry days during the relevant period, will be analyzed applying Poisson molding, which is appropriate for count data. The analysis is similarly as the analysis for the proportion of the heartburn-free days during the 8-week Treatment Period.

The exploratory efficacy parameters and proposed analysis methods are listed below:

Item No.	Efficacy Endpoints	Analysis Methods
1.	Percent change from baseline at Week 8 in WHSS	MMRM for change from baseline to Week 8.
2.	Overall Heartburn Responders with baseline WHSS ≥3	СМН
3.	Change from baseline of proportion of days when heartburn did not occur (DHSS = 0) or was very mild (DHSS = 1) during the 8-week Treatment Period	Analysis of covariance (ANCOVA)
4.	Proportion of days when heartburn did not occur (DHSS=0) or was very mild (DHSS=1) during the 8-week Treatment Period	Poisson regression for proportions
5.	Percent change from baseline at Week 8 in WRFS	MMRM for change from baseline to Week 8.

 Table 7:
 Exploratory Efficacy Parameters and Analysis Methods

Item No.	Efficacy Endpoints	Analysis Methods
6.	Change from baseline proportion of days when regurgitation did not occur (DRFS = 0) or rarely occurred (DRFS = 1) during the 8-week Treatment Period	ANCOVA
7.	Proportion of regurgitation free (DRFS = 0) days during the 8-week Treatment Period	Poisson regression for proportions
8.	Proportion of days when regurgitation did not occur (DRFS=0) or rarely occurred (DRFS=1) during the 8-week Treatment Period	Poisson regression for proportions

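### Heartburn-free days, the fourth alpha-controlled test: the SAP does not fix one model, and readings of Table 6 give a type I error from under 1% to over 70%

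*SAP*

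**What the plan says.** SAP 7.9.2 defines the endpoint as a proportion: "Proportion of heartburn-free days is calculated as the number of heartburn-free (DHSS = 0) days divided by the number of diary entry days". Table 6, row 3, then sets the analysis:

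- Model: "The data will be analyzed using the Poisson regression, which is appropriate for count data". The stated assumption is "Data following a Poisson distribution".
- Diary days enter "with the diary entry duration (in days) as a weight variable". Footnote a explains: "The weight variable weights the overdispersion parameter, which has the default value of 1".
- Estimate: "Model estimates in difference of incidence rate between the IW-3718 treatment group and placebo will be represented".
- Fallback: "In the case of overdispersion, a negative binomial model instead of Poisson regression will be implemented".

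SAP Table 7 applies the same method to the exploratory day-based endpoints under the label "Poisson regression for proportions". Protocol 3.7.4.3 has the same fallback and says only that diary days are adjusted for in the model, without saying how. Neither document names an offset. The test is fourth in a fixed sequence at two-sided 5% (SAP 6.6). SAP section 4 gives it 88% power, calculated with a two-sample t-test.

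**The concern.** Three things needed to run the test are left open.

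1. **The response.** The endpoint definition and Table 7 point to the proportion; Table 6 also speaks of counts and an incidence rate.
2. **The weight.** It could multiply each patient's log-likelihood, or divide the negative binomial dispersion parameter. Footnote a can be read either way.
3. **The switch.** No test or threshold is given, and nothing says which response and which use of diary days carry over.

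A log-link model also gives a rate ratio, while Table 6 promises a rate difference without saying how it is derived.

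This would matter little if every reading gave a test of about the right size. The Phase 2b figures in the SAP suggest otherwise. The plan claims family-wise control at 5% through this step, and a model settled only once the data are in hand gives no such control.

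**Working it through.** **Inputs from the documents.** SAP Table 1: placebo mean 0.195, SD 0.2822; IW-3718 mean 0.268, SD 0.2928. 330 per arm (section 4); about 550 in total, or 275 per arm (section 3.4). EE share 45% (section 4). Dropout about 10% (Appendix 1). Baseline window 14 days (section 7.9).

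**1. The plan's own figure.** Two-sample t-test (chi-square for the responder endpoint) powers at 330 per arm are 99.33%, 99.99%, 99.92% and 90.34%. Their product is 0.9933 × 0.9999 × 0.9992 × 0.9034 = 89.7%, against the stated 88%. So the figure reproduces as fixed-sequence t-test power. At 275 per arm the product is about 83%.

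**2. Poisson, closed form.** Variance/mean of the 56-day count:

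- placebo: 56 × 0.2822² / 0.195 = 22.9
- IW-3718: 56 × 0.2928² / 0.268 = 17.9

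With model-based standard errors the type I error is 2 × [1 − Φ(1.96/√φ)]. That is 64% for φ = 17.9 and 68% for φ = 22.9. A Poisson fit of the proportion weighted by diary days has the same score equations and information as the count with a log-days offset, so it has the same error.

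**3. Negative binomial on the proportion, likelihood weight.** Negative binomial variance cannot fall below its mean. Here the variance is 0.2822² = 0.080 against a mean of 0.195 (ratio 0.41), and in the active arm the ratio is 0.32. The dispersion estimate goes to zero and the fit reverts to weighted Poisson.

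**4. Negative binomial on the count, likelihood weight.** Each patient counts about 50 times, so standard errors shrink by about √50. Then 1.96/√50 = 0.277, a two-sided tail of 78%. The unweighted model is itself conservative, which brings this down somewhat.

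**5. Simulation.** Beta-binomial data matched to Table 1, with 3,000 null and 2,000 alternative trials per cell. Assumed, not in the documents: 5% missed entries, 60% of patients with WHSS ≥3, baseline mean 0.07, and the correlation r between baseline and on-treatment proportions.

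Type I error (%), 330 per arm:

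| Model | No covariates | r 0.35 | r 0.55 |
|---|---|---|---|
| Poisson, proportion + weight | 67 | 66 | 62 |
| NB, proportion + likelihood weight | 67 | 66 | 62 |
| NB, count + likelihood weight | 72 | 73 | 75 |
| NB, proportion, weight divides dispersion | 0.4 | 0.2 | 0.0 |
| NB, count, weight divides dispersion | 1.3 | 2.6 | 2.6 |
| NB, count + log-days offset | 1.1 | 1.8 | 2.5 |
| Offset + sandwich SEs | 5.4 | 5.6 | 5.0 |
| ANCOVA on proportion, HC3 | 5.1 | 5.2 | 5.1 |

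Monte Carlo error at 5% is √(0.05 × 0.95/3000) = 0.4 points. At 275 per arm every figure is within 3 points of these.

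Power (%), same three columns:

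| Model | 330 per arm | 275 per arm |
|---|---|---|
| NB, count + offset | 75 / 85 / 94 | 64 / 76 / 87 |
| NB, proportion, weight divides dispersion | 49 / 50 / 52 | – |
| Offset + sandwich SEs | 89 / 92 / 95 | 84 / 86 / 90 |
| ANCOVA, HC3 | 91 / 93 / 97 | 86 / 88 / 93 |

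**6. Sensitivity.** With a logit-normal shape instead of beta, the null results were 63–67% (NB, proportion + likelihood weight), 74–78% (NB, count + likelihood weight), 1.3–3.7% (NB + offset) and 4.2–5.3% (sandwich). With about 93% diary completion, 50% of patients with WHSS ≥3 and baseline correlation 0.5, they were 62–64%, 73–76%, 1.5–2.8% and 4.4–5.9%. In that last set, Poisson on the raw count weighted by days reached about 95%.

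**The case against.** The plan foresees overdispersion. Pearson dispersion was at least 13.5 in all 22,500 null trials, so any usual rule would trigger the switch. The Poisson figures would then not be the reported result, and the missing threshold has little practical effect. The weight is no fault in the Poisson model itself, since it is equivalent to an offset there. Several negative binomial readings, including the conventional count with offset, keep type I error below 5%. The figures above 70% need the count as response together with a likelihood weight, which is not the reading the endpoint definition favours. Naming the count and an offset while keeping the switch would also protect alpha.

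All of this is correct, but it does not clear the text. The offset form is not what the SAP specifies. On the response that the text favours, the likelihood-weight reading still gives 62% to 68% after the switch. The other reading on that response gives under 1%, with about 50% power. Count plus offset with the switch is safe for alpha but conservative, and it loses up to 14 power points at 330 per arm (75% against 89%). The disclosed t-test power is not an error in itself; it simply was not computed for the planned model.

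**Conclusion.** The concern holds. The analysis of the fourth alpha-controlled endpoint rests on a distribution that the SAP's own Table 1 contradicts, and the stated fallback does not reliably repair it. After the switch, type I error lies between about 0% and 78% depending on how the response and the weight are read.

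The Poisson result (64% to 68%) and the collapse of the negative binomial on the proportion follow from Table 1 alone. The other percentages rest on the simulation assumptions listed above; type I error barely moved when these changed, while negative binomial power did. With the planned covariates, negative binomial plus offset gives 85% and 94% at 330 per arm, either side of the stated 88%.

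The harm is confined to the last test, reached only after three rejections. It should be fixed, but it does not touch the primary analysis.

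**What to change.** Rewrite Table 6, row 3, to name one model with valid variance:

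- Response: each patient's number of heartburn-free days.
- Model: log-linear (Poisson mean) with log(number of diary entry days) as offset.
- Terms: treatment, baseline EE status, baseline WHSS (<3, ≥3) and baseline proportion of heartburn-free days.
- Inference: sandwich standard errors. Report the rate ratio and the standardized rate difference, with 95% CIs from the same robust covariance.

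Delete the weight, footnote a, the Poisson assumption and the negative binomial switch.

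An acceptable alternative is ANCOVA on the proportion with HC3 standard errors. It gives the difference directly but counts short diaries equally with full ones. Weighting that linear model by diary days, still with HC3, removes the drawback (type I error 5.5 / 5.2 / 5.0%, power 90 / 92 / 97% at 330 per arm, columns as in the tables). Choose one and name it.

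Align protocol 3.7.4.3 or record the departure, carry the change to the Table 7 endpoints that borrow this method, and restate power for the chosen model at the sample size that applies (660 or about 550). As a separate matter, settle whether a heartburn-free day is judged on Item 1 alone (SAP Table 3, 5.2.2, Appendix 1) or on DHSS = 0 (7.9.2).

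The cost is one table row, a matching protocol change and a few lines of code. No new data are needed.

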7.9.3. Exploratory Efficacy Parameters

Exploratory efficacy parameters will be explored outside of the formal testing procedures and not controlled for multiplicity. The mITT Population will be used for the analyses. If appropriate, for selected efficacy parameters, the SA Population will be used for sensitivity analysis. The baseline definitions for different type of parameters can be found in Section 7.9.

- Change or percent change continuous parameters will be analyzed using the MMRM approach like the primary efficacy parameter, WHSS change from baseline.
- Categorical responder parameters will be analyzed utilizing the CMH testing method that is proposed for the secondary efficacy analysis for OHR.
- Time dependent proportion parameters, defined as days the event of interesting occurs divided by the number of eDiary entry days during the relevant period, will be analyzed applying Poisson molding, which is appropriate for count data. The analysis is similarly as the analysis for the proportion of the heartburn-free days during the 8-week Treatment Period.

The exploratory efficacy parameters and proposed analysis methods are listed below:

Item No.	Efficacy Endpoints	Analysis Methods
1.	Percent change from baseline at Week 8 in WHSS	MMRM for change from baseline to Week 8.
2.	Overall Heartburn Responders with baseline WHSS ≥3	СМН
3.	Change from baseline of proportion of days when heartburn did not occur (DHSS = 0) or was very mild (DHSS = 1) during the 8-week Treatment Period	Analysis of covariance (ANCOVA)
4.	Proportion of days when heartburn did not occur (DHSS=0) or was very mild (DHSS=1) during the 8-week Treatment Period	Poisson regression for proportions
5.	Percent change from baseline at Week 8 in WRFS	MMRM for change from baseline to Week 8.

 Table 7:
 Exploratory Efficacy Parameters and Analysis Methods

Item No.	Efficacy Endpoints	Analysis Methods
6.	Change from baseline proportion of days when regurgitation did not occur (DRFS = 0) or rarely occurred (DRFS = 1) during the 8-week Treatment Period	ANCOVA
7.	Proportion of regurgitation free (DRFS = 0) days during the 8-week Treatment Period	Poisson regression for proportions
8.	Proportion of days when regurgitation did not occur (DRFS=0) or rarely occurred (DRFS=1) during the 8-week Treatment Period	Poisson regression for proportions
9.	 Overall Regurgitation Responder: a patient who is a Weekly Regurgitation Responder for at least 4 weeks, including at least 1 of the last 2 weeks (Weeks 7 and 8), during the 8-week Treatment Period A Weekly Regurgitation Responder is a patient with a decrease of 	СМН
	 ≥45% from baseline in WRFS A patient who reports DRFS for less than 4 days during a week will not be considered a Weekly Regurgitation Responder for that week 	
10.	Change from baseline to Week 8 in each mRESQ item	MMRM for change from baseline to Week 8.
11.	Proportion of nights with difficulty falling asleep due to GERD during the 8-week Treatment Period	Poisson regression for proportions
12.	Proportion of days with nighttime awakening (≥ 1 time) due to GERD during the 8-week Treatment Period	Poisson regression for proportions
13.	 Degree of relief of heartburn/regurgitation/overall GERD symptoms responder: Degree of relief responder: patient who reported a score of 1-Significantly Relieved or 2-Moderately Relieved on the Degree of Relief question for at least 4 weeks, including at least 1 of the last 2 weeks (Weeks 7 and 8), during the 8-week Treatment Period 	СМН
14.	Change from baseline at Week 8 in heartburn/regurgitation/overall GERD symptoms bothersomeness	MMRM for change from baseline to Week 8.
15.	Proportion of days with rescue medication use during the 8-week Treatment Period	Poisson regression for proportions
16.	Erosive esophagitis (EE) healed (not present) at Week 8	CMH (the central reads and the local reads will be analyzed, respectively)

Item No.	Efficacy Endpoints	Analysis Methods
17.	Proportion of patients with erosive esophagitis (EE) improved by at least 1 grade at Week 8	CMH (the central reads and the local reads will be analyzed, respectively)

Descriptive supportive summary for following variables will be generated for SA population.

Item No.	Description of Summary
1.	Percent change from baseline in WHSS by week
2.	Percent change from baseline in WRFS by week
3.	Change from baseline in WHSS by week
4.	Change from baseline in WRFS by week
5.	Change from baseline in each mRESQ item by week
6.	Proportion of heartburn-free (DHSS=0) days by week
7.	Proportion of regurgitation-free (DRFS=0) days by week
8.	Proportion of days when heartburn did not occur (DHSS=0) or was very mild (DHSS=1) by week
9.	Proportion of days when regurgitation did not occur (DRFS=0) or rarely occurred (DRFS=1) by week
10.	Proportion of nights with difficulty falling asleep due to GERD by week
11.	Proportion of days with nighttime awakening (≥ 1 time) due to GERD by week
12.	Proportion of days with rescue medication use by week
13.	Degree of relief of heartburn/regurgitation/overall GERD symptoms by week
14.	Heartburn/regurgitation/overall GERD symptoms bothersomeness by week
15.	Treatment satisfaction by week
16.	Shift in erosive esophagitis (EE) grade from baseline to Week 8

7.10. Safety Analysis

All safety parameters will be summarized using descriptive statistics. Safety analyses will be performed on the Safety Population. The safety parameters will include AEs, clinical laboratory evaluations, vital signs, ECGs, and physical examination. For each safety parameter, the last non-missing assessment made before the first dose of study drug will be used as the baseline for all analyses of that safety parameter.

The treatment group designation for safety summaries is based on the treatment the patient actually received. The "treatment actually received" for a patient who received treatment other

than the assigned treatment (even if only a single dose) during the treatment period will be defined as the treatment of which the patient actually took, regardless of the treatment assigned.

7.10.1. Adverse Events

AEs will be coded by system organ class and preferred term using the MedDRA dictionary, version 23.0 which contains the COVID-19 specific terms. An AE will be considered a treatment-emergent AE (TEAE) if the AE started after initial study drug administration and within 1 day of the last dose of study drug. In addition, an AE that started before initial study drug but worsened after the first dosing of the study drug is also considered a TEAE.

The number and percentage of patients reporting TEAEs in each treatment group will be tabulated:

- by system organ class (SOC) and preferred term (PT)
- by SOC, PT, and severity
- by SOC, PT, and relationship to study drug.

If a patient has more than one TEAE coded to the same PT, the patient will be counted only once for that PT by identifying those TEAEs with the highest severity and the closest relationship to study drug.

The incidence of the following TEAEs will be summarized by PT:

- Most frequent ($\geq 2\%$ of patients in any treatment group) TEAEs
- Treatment Emergent SAEs
- TEAEs leading to premature discontinuation of study drug.

All AE summary tables will be SOC sorted alphabetically and have PT within each SOC sorted by decreasing frequency for IW-3718 group.

A TEAE summary table with all the non-SAEs by SOC and PT will be generated to support the clinicaltrials.gov reporting purpose.

AE listings will be presented for all patients with AEs, screened patients with SAEs, patients with AEs leading to discontinuation, all SAEs (no matter it is treatment-emerge or not) and patients who died (if any), respectively.

7.10.2. Clinical Laboratory Parameters

Descriptive statistics for clinical laboratory values (in SI units) and changes from the baseline values at each assessment time point will be presented by treatment group for each clinical laboratory parameter. All laboratory data will be listed. The clinical laboratory parameters are listed in Section 5.5.6.

For each clinical laboratory parameter, the number and percentage of patients with potentially clinically significant (PCS) postbaseline clinical laboratory values will be tabulated by treatment group for data collecting no more than 1 day after the last dose. The criteria for PCS laboratory values are described in Table 8. The percentages will be calculated relative to the number of patients with available non-PCS baseline values and at least 1 post-baseline assessment. The

potential numerator will be the total number of patients with available non-PCS baseline values and at least 1 post-baseline PCS value in the corresponding postbaseline period.

A supportive listing for patients with PCS postbaseline values will be provided, including the PID number, study center, baseline and postbaseline values for each visit, and a flag indicating the PCS laboratory values.

Parameter	SI Unit	Lower Limit	Higher Limit
CHEMISTRY	· ·		I
Albumin	g/L	<0.9 × LLN	>1.1 × ULN
Alanine aminotransferase	U/L	_	$\geq 3 \times ULN$
Alkaline phosphatase	U/L	_	$\geq 3 \times ULN$
Aspartate aminotransferase	U/L	_	$\geq 3 \times ULN$
Bicarbonate	mmol/L	<0.9 × LLN	>1.1 × ULN
Bilirubin, total	μmol/L	_	>1.5 × ULN
Calcium	mmol/L	<0.9 × LLN	>1.1 × ULN
Chloride	mmol/L	<0.9 × LLN	>1.1 × ULN
Cholesterol, total	mmol/L		>1.6 × ULN
Creatinine	μmol/L	_	>1.3 × ULN
Glucose	mmol/L	<0.8 × LLN	>1.4 × ULN
Magnesium	mmol/L	<0.9 × LLN	>1.1 × ULN
Phosphate	mmol/L	<0.9 × LLN	>1.1 × ULN
Potassium	mmol/L	<0.9 × LLN	>1.1 × ULN
Protein, total	g/L	<0.9 × LLN	>1.1 × ULN
Sodium	mmol/L	<0.9 × LLN	>1.1 × ULN
Urea nitrogen	mmol/L	_	>1.2 × ULN
Uric acid	µmol/L	<0.9 × LLN	>1.1 × ULN
HEMATOLOGY	· ·		
Basophils, absolute cell count	10 ⁹ /L	_	>3 × ULN
Eosinophils, absolute cell count	10 ⁹ /L		>3 × ULN
Hematocrit	Ratio	<0.9 × LLN	>1.1 × ULN

 Table 8:
 Criteria for Potentially Clinically Significant Laboratory Results

Parameter	SI Unit	Lower Limit	Higher Limit
Hemoglobin	g/L	<0.9 × LLN	>1.1 × ULN
Lymphocytes, absolute cell count	10 ⁹ /L	<0.8 × LLN	>1.5 × ULN
Mean corpuscular hemoglobin	Pg	_	>3 × ULN
Mean corpuscular hemoglobin concentration	g/L	_	>3 × ULN
Mean corpuscular volume	fL	<0.9 × LLN	>1.1 × ULN
Monocytes, absolute cell count	10 ⁹ /L	_	$>3 \times ULN$
Neutrophils, absolute cell count	10 ⁹ /L	<0.8 imes LLN	>1.5 × ULN
Platelet count	10 ⁹ /L	<0.5 × LLN	>1.5 × ULN
Red blood cell count	10 ¹² /L	<0.9 × LLN	>1.1 × ULN
White blood cell count	10 ⁹ /L	<0.7 × LLN	>1.5 × ULN

LLN = lower limit of normal value provided by the laboratory; SI = Le Système International d'Unités (International System of Units); ULN = upper limit of normal value provided by the laboratory.

